expectations questionnaire at baseline; PESQ = patient experience and satisfaction questionnaire; PET = Positron emission tomography; PK = Pharmacokinetic; PR = Partial response; PS = Performance status; PT = Prothrombin time; PTT = partial thromboplastin time; RNA = ribonucleic acid; RR = respiratory rate; sCR = stringent complete response; SC = Subcutaneous; SGOT = Serum glutamate-oxalate transferase; SGPT = Serum glutamate-pyruvate transferase; sFLC = Serum free light chain; SAE = serious adverse event; SPEP = Serum M-protein immunoelectrophoresis; TSH = Thyroid stimulating hormone; VGPR = Very good partial response; UPEP = Urine M-protein immunoelectrophoresis.

- a **Evaluation:** Assessments to be performed prior to study treatment/premedication administration unless otherwise indicated. Results should be reviewed by the Investigator.
- b **Randomization:** To take place once the consented participant has completed all the necessary screening procedures and is deemed eligible (based on assessments including myeloma specific results from central laboratory (see footnote "bb") and hematology/biochemistry local laboratory results) for randomization by the investigator or designee. All eligible participants must be randomized by contacting the Interactive Response Technology (IRT). Every effort should be made to start treatment within 3 working days of randomization.
- c **Day 1 and Day 15 (28-day cycle [± 3 day]):** Day 1 of Cycle 1 refers to the day the participants receive the first dose of study treatment administration. Day 1 of Cycle 2 corresponds to D29 of Cycle 1. Day 1 of each subsequent cycle corresponds to Day 29 (± 3 day) of the previous cycle. Day 8 and Day 22 window (± 1 day).

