Co-Primary endpoint	ORR [stringent complete response (sCR), complete response (CR), very good partial response (VGPR), and partial response (PR)].	ITT	While not initiating new anti-cancer therapy Regardless of IMP discontinuation (treatment policy strategy).	This endpoint will be analyzed by calculating the relative risk between the SC and IV arm and its two-sided 95% CI using Farrington-Manning method and compare its lower CI limit with the pre-defined margin. In absence of confirmed PR or better, participants will be considered as non-responders, whatever the reason (including participants with missing or non-evaluable best overall response).
Co-primary endpoint	C_{trough} at steady state (corresponding to predose at C6D1).	PK-PP	(Principal Stratum strategy) Doses, administration scheme, sample collection, processing and result, time window of collection and adequate documentation.	The point estimate (ratio of geometric means for C_{trough} at steady state of SC/IV) together with its two-sided 90% CI will be calculated. The lower bound of the 90% CI will be compared with 80%. Participants who do not have all administrations up to C5D15 (one dose omission permitted at C1 only) and PK sample collected out of the prespecified time window are not included into the analysis population.

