6.5 DOSE MODIFICATION

Dose modifications are permitted according to the guidelines described in this section.

The participant may have a dose omitted for any IMP within a cycle if toxicity occurs and the participant does not recover within 3 days after the planned day of planned infusion/administration. If a participant experiences several toxicities and there are conflicting recommendations, the most conservative dose adjustment recommended (dose reduction/omission/delay appropriate to the most severe toxicity) should be followed. Within a cycle, the treatment window is ± 1 day for each of QW IMP administrations and ± 3 days for each of Q2W IMP administrations.

Cycle delays are permitted in case of toxicity (see [Section 6.5.7](#)). Cycle is considered delayed if Day 1 is performed more than 3 days after the planned Day 1 of this cycle. Once a dose of IMP has been decreased, intra-participant re-escalation back to the previous dose level is not permitted, except for dexamethasone dose reduction in a context of intercurrent condition neither related to dexamethasone adverse event nor related to multiple myeloma that might require a transient dose reduction. If a dose reduction is required, it is to be applied compared to the last dose level received by the participant.

Administration of the IMP will be discontinued in the event of an AE that persists despite appropriate dose modifications or any other AE that, in the opinion of the Investigator, warrants discontinuation.

All changes to study treatment administration must be recorded in the eCRF. Participants will receive the next cycle of study treatment after recovery of the toxicity as described below. If one of the IMPs is permanently discontinued, the other IMPs can be continued until PD, unacceptable toxicity, or participant's wish to discontinue further study treatment. The end of study treatment in this case will be 30 days after the date of the last study treatment administration.

Recommendations for dose adjustments of IMPs due to AEs are described in [Table 13](#), [Table 14](#), [Table 15](#) (SC arm) and [Table 16](#).

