- b For participants with plasma cells $> 50\%$ of bone marrow nucleated cells at baseline, to initiate Cycle 2, platelet counts should be $\geq 30\,000/mm^3$ regardless response status at end of Cycle 1. During Cycles 2-4, platelet counts should be $\geq 30\,000/mm^3$, if last response is not better than SD, but if last response is PR or better during Cycles 2-4, D1 next cycle can be administered only if platelet counts $\geq 50\,000/mm^3$. For D1 administration beyond Cycle 4, platelet counts should be $\geq 50\,000/mm^3$.
- c A dose delay of up to 14 days between cycles is permitted in order to recover to the participant's baseline status. Beyond 14 days, the participant should be discontinued from study treatment, unless there is strong evidence of clinical benefit to justify continuation of dosing with study treatment (see [Section 6.5.7](#)).
- d If G4 neutropenia, assess ANC every 2-3 days until ANC $\geq 0.5 \times 10^9/L$ and at least weekly thereafter until ANC $\geq 1.0 \times 10^9/L$.

IV: intravenous.
SC: subcutaneous.
PO: per os.

Dose adjustments for participants treated with isatuximab, pomalidomide and dexamethasone combination in the case of non-hematological adverse reaction are shown in [Table 14](#).

Table 14 - Guidelines for dose adjustments for non-hematologic toxicities - isatuximab/pomalidomide/dexamethasone combination

Adverse event	Recommended action		
	Isatuximab^c	Dexamethasone^c	Pomalidomide
DVT/PE			
Grade 3	
Day 1 of cycle: initiate appropriate anticoagulation therapy and when efficient anticoagulation administer cycle at full dose isatuximab and the same dose level of dexamethasone and pomalidomide^a.
 
Within cycle: maintain full dose isatuximab and the same dose level of dexamethasone as planned. For pomalidomide:
 
 First episode: hold pomalidomide, initiate appropriate anticoagulation therapy and restart same dose pomalidomide when efficient anticoagulation. Second episode: despite appropriate anticoagulation pomalidomide permanently discontinued. 		

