8.2 EFFICACY ASSESSMENTS

The primary and secondary efficacy endpoints will be determined by IRC based on central laboratory M-protein analysis, local BM for plasma cell infiltration assessment as recorded in the electronic case report form (eCRF) and central radiology review according to IMWG criteria ([Section 10.10](#), Appendix 10). IRC will be blinded to treatment assignment. Please see the schedule of activities for more information ([Section 1.3](#)).

The following myeloma-specific lab tests will be performed at screening (for eligibility) and again within 24 hours prior to the start of study treatment administration at Cycle 1/Day 1 (baseline for response assessment) and then Day 1 of every cycle during treatment up to progression and for participants who discontinue study treatment for reasons other than progression, every 4 weeks during follow-up until PD:

- M-protein quantification (serum and 24-hour urine, protein immunoelectrophoresis, and immunofixation) by central laboratory. After Cycle 1/Day 1, immunofixation will be done in case of undetectable M-protein (serum and urine).
- Serum free light chain levels by central laboratory.
- Quantitative immunoglobulins (IgG, IgA, IgM, IgD, and IgE) by central laboratory.

Other examinations for disease assessment will be done as below:

- Bone marrow aspiration (BMA) (or biopsy as clinically indicated) for quantification of percentage plasma cells is required at screening/baseline (within 21 days prior to study treatment administration). Repeat BM aspirate or biopsy to confirm CR or sCR if CR or sCR is suspected (local laboratory).
- Bone marrow aspiration for MRD assessment: At screening, at time of maximum confirmed CR or VGPR, 12 months after C1D1 and 12 months after first MRD negativity.
- Bone marrow aspiration for cytogenetics assessment: At screening, bone marrow aspirate will be collected for Fluorescent in Situ Hybridization (FISH) (including, but may not be limited to, del[17p], t[4;14], t[14;16]), 1q21+) analyses in central laboratory.
- Bone marrow aspiration for genomic and genetic profiling at screening and at time of progression (central laboratory).

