10.11 APPENDIX 11: IMWG RESPONSE CRITERIA

Disease response will be assessed using the updated International Myeloma Working Group Response Criteria (IMWG) (42). A confirmation assessment for disease response within 4 weeks is required in this protocol (either PR or better, or PD).

Table 22 - Adapted from updated International Myeloma Working Group response criteria

IMWG MRD criteria (requires a complete response as defined below)	
Sustained MRD-negative	MRD negativity in the marrow (NGF or NGS, or both) and by imaging as defined below, confirmed minimum of 1 year apart. Subsequent evaluations can be used to further specify the duration of negativity (eg, MRD-negative at 5 years).
Flow MRD-negative	Absence of phenotypically aberrant clonal plasma cells by NGF on bone marrow aspirates using the EuroFlow standard operation procedure for MRD detection in multiple myeloma (or validated equivalent method) with a minimum sensitivity of 1 in 10^5 nucleated cells or higher.
Sequencing MRD-negative	Absence of clonal plasma cells by NGS on bone marrow aspirate in which presence of a clone is defined as less than two identical sequencing reads obtained after DNA sequencing of bone marrow aspirates using the LymphoSIGHT platform (or validated equivalent method) with a minimum sensitivity of 1 in 10^5 nucleated cells or higher.
Imaging-positive MRD-negative	MRD negativity as defined by NGF or NGS plus disappearance of every area of increased tracer uptake found at baseline or a preceding PET/CT or decrease to less mediastinal blood pool SUV or decrease to less than that of surrounding normal tissue.
Standard IMWG response criteria	
Response	IMWG criteria
CR	
• Negative immunofixation on the serum and urine and,• Disappearance of any soft tissue plasmacytomas.

- <5% plasma cells in bone marrow aspirates and,
- A normal FLC ratio of 0.26–1.65 is required for FLC disease only.

Two consecutive assessments are needed. No known evidence of progressive disease or new bone/soft tissue lesions if radiographic studies were performed

CR as defined above plus:

- Normal FLC ratio (0.26 to 1.65) and,
- Absence of clonal cells in bone marrow biopsy by immunohistochemistry (κ/λ ratio $\leq 4:1$ or $\geq 1:2$ for κ and λ patients, respectively, after counting ≥ 100 plasma cells).

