- Appearance of new lesion(s), $\geq 50\%$ increase from nadir in SPD of >1 lesion, or $\geq 50\%$ increase in the longest diameter of a previous lesion >1 cm in short axis.

Two consecutive assessments are needed for serum and or urine. If radiological progression is documented, no need to repeat the assessment.

Abbreviations: CR = complete response; FLC = free light chain; IMWG = International Myeloma Working Group; M = monoclonal; MRD = minimal residual disease; NGF = next-generation flow; NGS = next-generation sequencing; PD = progressive disease; PR = partial response; sCR = stringent complete response; SD = stable disease; SPD = sum of the products of the maximal perpendicular diameters of measured lesions; SUV = maximum standardized uptake value; VGPR = very good partial response.

A plasmacytoma that has been radiated is not suitable for response assessment; however, it must be monitored to assess for progressive disease.

For participants achieving VGPR by other criteria, a soft tissue plasmacytoma must decrease by more than 90% in the sum of the products of the maximal perpendicular diameters of measured lesions (SPD) compared with baseline.

For IgA and IgD myeloma, quantitative immunoglobulin measurements are preferred for assessments, the same percentage changes apply for serum M-spike (see table above).

Definite increase in the size of existing bone lesions or soft tissue plasmacytomas is defined as below:

- $\geq 50\%$ increase in the size of at least one bidimensionally measurable lesion (in comparison with the measurements at Nadir) or appearance of a new lesion.
- Pathological fracture or collapse of bone are not necessarily evidence of disease progression.

Reminder: definitions of Response and Progression are based on IMWG Uniform Reporting Criteria:

- Any response category (sCR, CR, VGPR, PR, and MR) or progression needs to be confirmed by two consecutive disease assessments according to the Study Flow Chart. A disease assessment at one time point not matched by the same disease assessment at the next time point will be considered unconfirmed (except for progression by imaging, bone marrow PC counts, where one time point is adequate for confirmed response or progression).
- Urine M-protein is not needed to document PR or minor response if baseline urine M-protein was not measurable; however, it is still required for CR and VGPR.

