- Documentation of response requires two consecutive readings of the applicable disease parameter (serum M-protein, urine M-protein or serum FLC), performed at any time (no minimum interval is required, it can be done the same day); however, to confirm response or progressive disease, two discrete samples are required; testing cannot be based upon the splitting of a single sample.
- Participants will continue in the last confirmed response category until there is confirmation of progression or improvement to a higher response status; participants cannot move to a lower response category.
- Percent decreases for response calculations are from baseline values (Cycle 1, Day 1).
- Percent increases for progression calculations are from lowest response values or baseline values, whichever is the smaller number. The lowest value does not need to be confirmed.
- The lowest confirmed value before suspected progression will be used as baseline for calculation of progression; if a serum and/or urine spike is considered too low to quantitate, this value can be assigned as zero as a baseline for documentation of subsequent progressive disease. Participants will be considered to have progressive disease

if they meet the criteria for progression by a variable that was not considered measurable at baseline; however, for participants who had a measurable serum or urine M-spike at baseline, progression cannot be defined by increases in serum FLC alone.

Radiographic and BM assessments do not need to be confirmed.

Participants with measurable serum and/or urine M-protein and/or sFLC during screening, but below level of eligibility on efficacy laboratory performed on Cycle 1 Day 1
(eg, participants with M-protein value >0 [or IF positive] and <0.5 g/dL):

- These participants can have only 3 possible overall responses: **CR, non-PD, or PD**.
- Participants with previous measurable M-protein (urine and/or serum) but at Cycle 1 Day 1 below the level of measurability and no measurable sFLC can have CR, non-PD, or PD responses only according to the increase or decrease of M-protein or extra/para medullary soft tissue plasmacytoma if applicable, following the IMWG criteria.
- If measurable sFLC at Cycle 1 Day 1, the participant will be followed on this value, based on IMWG criteria.

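### Appendix 11 gives two conflicting rules for confirming a response, and the 4-week one cannot be reliably met by the trial's own 28-day (±3) schedule

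*Protocol*

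**What the plan says.** **Rule with a limit.** The opening paragraph of Appendix 11 states: "A confirmation assessment for disease response within 4 weeks is required in this protocol (either PR or better, or PD".

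**Rule without a limit.** The reminder list below Table 22 says each response category or progression "needs to be confirmed by two consecutive disease assessments according to the Study Flow Chart". It calls a result unconfirmed when the next time point does not match it. Imaging and bone marrow findings are exempt. Table 22 asks for two consecutive assessments for PR and better, and for serum or urine progression, and gives no interval. The PFS definition in Table 6 likewise asks for two consecutive assessments for paraprotein progression.

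**Related bullet.** The same list adds: "Documentation of response requires two consecutive readings of the applicable disease parameter". It waives any minimum interval and requires two discrete samples to confirm.

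**Schedule.**
- Section 8.2: the myeloma tests are done at baseline, "then Day 1 of every cycle during treatment up to progression".
- Table 1, footnote c: "Day 1 of each subsequent cycle corresponds to Day 29" of the previous cycle, with a window of ±3 days.
- Section 6.5: "Cycle is considered delayed if Day 1 is performed more than 3 days after the planned Day 1 of this cycle".
- Table 13, footnote c: "A dose delay of up to 14 days between cycles is permitted". Section 6.5.7 allows longer after discussion with the sponsor.

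**Consequence.** Table 7, for the ORR co-primary endpoint: "In absence of confirmed PR or better, participants will be considered as non-responders, whatever the reason".

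**The concern.** Take a participant with a PR on one Day 1 and the same finding on the next Day 1, 29 days later. Both visits are on schedule. Under the reminder list the response is confirmed. Under the opening paragraph it is not, and Table 7 then makes the participant a non-responder unless a later pair qualifies. The protocol does not say which rule governs.

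The rule decides who counts as a responder in the efficacy co-primary endpoint and in the first key secondary endpoint (VGPR or better). It also sets dates. TT1R and DOR start from a response that is later confirmed, so a failed first pair moves the start to a later visit. The progression half of the rule affects PFS and the end of DOR, not ORR.

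**Working it through.** **1. Gaps that the schedule permits**

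| Situation | Gap between adjacent Day 1 draws | Against 28 days |
|---|---|---|
| On window | 28 ± 3 = 25 to 31 days | 29, 30 and 31 exceed it: 3 of 7 permitted days |
| Delayed cycle | 28 + 4 = 32 to 28 + 14 = 42 days | always exceeds it |

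Table 1, footnote bb, schedules no serum draw between Day 1 visits. Section 8 allows repeat or unscheduled samples for safety or technical reasons and does not mention confirmation. The schedule therefore provides no visit that would ensure the limit is met.

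**2. Chance that one pair misses the limit**

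The documents give neither the spread of visits within the window nor a delay rate, so both are assumed. Let f be the chance that an on-window gap exceeds 28 days and d the share of cycles delayed. The chance that a pair fails is q = d + (1 − d) × f.

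- Visits spread evenly over the window: f = 3/7 = 0.43.
- 70% of visits exactly on day 28, the rest spread evenly: f = 0.30 × 3/7 = 0.13.

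**3. Chance that a lasting responder is never confirmed**

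A responder is lost to ORR only if every adjacent pair fails. With k independent pairs that chance is q^k.

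| Assumption | q | 1 pair | 2 pairs | 3 pairs | 5 pairs |
|---|---|---|---|---|---|
| Even spread, d = 0 | 0.429 | 43% | 18% | 8% | 1.5% |
| Even spread, d = 0.20 | 0.543 | 54% | 30% | 16% | 4.7% |
| 70% on day, d = 0 | 0.129 | 13% | 1.7% | 0.2% | about 0% |
| 70% on day, d = 0.20 | 0.303 | 30% | 9% | 2.8% | 0.3% |

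The loss is appreciable only where one or two assessments follow the first response.

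**4. Power: the plan's figure first**

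Inputs from Section 9.5: 267 per arm, IV ORR 0.604, true ratio 1.02 (SC ORR 0.604 × 1.02 = 0.6161), margin R = exp(0.6 × ln 0.7463) = 0.839, one-sided alpha 0.025.

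Farrington-Manning score test for a ratio:
- Constrained rates under p_SC = R × p_IV: 0.5495 (SC) and 0.6550 (IV).
- Null SE = √[(0.5495 × 0.4505 + 0.839² × 0.6550 × 0.3450)/267] = 0.0390.
- SE under the alternative = √[(0.6161 × 0.3839 + 0.839² × 0.604 × 0.396)/267] = 0.0389.
- z = (0.6161 − 0.839 × 0.604 − 1.96 × 0.0390)/0.0389 = 0.84, so power is 80.05%.

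This reproduces the stated figure of approximately 80%.

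**5. Power if the limit removed the same share of responders in both arms**

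Both rates are multiplied by (1 − loss), so the ratio stays at 1.02. The loss fractions are assumptions.

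| Responders lost | IV ORR | Power |
|---|---|---|
| 0% | 60.4% | 80.05% |
| 1% | 59.8% | 79.1% |
| 2% | 59.2% | 78.1% |
| 5% | 57.4% | 75.0% |
| 10% | 54.4% | 69.8% |

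**The case against.** The best defence is that the reminder list already defines an unconfirmed result by the next time point and not by elapsed days. Nothing says a match after day 28 is void. Table 1, footnote ee, itself speaks of a 4-week cycle with a ±3-day window, so the 4-week phrase may only mean the next cycle. End-of-treatment retesting is triggered partly by tests more than 4 weeks old, which suggests later confirmation was expected. The review committee works to a charter that is not at hand and may settle the matter. All this makes the next-visit reading plausible. It does not remove the sentence, which calls its limit a requirement of this protocol and mentions no window.

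Several stronger readings are tempting but not supported:

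- *Responders will often be lost.* The 43% rests on an even spread of visits. The 84.9% with Grade 3 or higher neutropenia in the ICARIA-MM IsaPd arm is the share of participants affected, not a rate of delayed Day 1 visits.
- *The SC/IV ratio will be biased.* The Phase 1b pomalidomide dose intensity of 69.2% comes from the 10-participant pump cohort. The injector cohort (22 participants), which used the type of device in this trial, had 85.4%, against 93.5% for IV. Dose intensity is also not a delay rate, and no delay rate by arm is given.
- *The bullet on two readings contradicts the 4-week limit.* It waives a minimum interval only. The conflict is with the next-time-point rule.
- *End-of-treatment timing lowers ORR.* That visit falls 25 to 35 days after the last dose, or earlier if new therapy starts. The clearest case it affects is confirmation of progression, which bears on PFS and DOR.

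**Conclusion.** The point holds as an unresolved contradiction in how a co-primary endpoint is defined. The two rules classify an on-window pair at 29 to 31 days differently, as they do any pair after a permitted delay. Applied literally, the 4-week rule would leave on-schedule pairs unconfirmed.

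Misclassification is a risk under one of two readings, not a certainty, and the documents do not fix its size. With no delays, single-pair failure is about 13% to 43%; delays raise it. It falls quickly with further pairs, so ORR loss would be confined mainly to short responses and to first responses close to the primary cut-off. For lasting responders the likelier effect is a later response date.

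Equal loss leaves the ratio unchanged and costs power: about 2 percentage points if 2% of responders were lost, from a design with nothing in hand above 80%. Unequal loss could move the ratio, but nothing in the protocol shows it. The stated sample size calculation is not in error.

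**What to change.** In the opening paragraph of Appendix 11, replace the 4-week limit with: *at the next consecutive scheduled disease assessment (including the visit window and permitted cycle delays), on a separate sample*. This agrees with the next-time-point rule and the two-discrete-samples rule in the reminder list. Keep the existing exemption for imaging and bone marrow findings.

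For response only, refer to the Table 7 strategy for new anti-cancer therapy. Do not attach that condition to progression, because assessments continue to progression even after further therapy starts.

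Use the same wording in the review committee charter. If a 28-day limit is really intended, Table 1 would need a confirmation draw inside it, which it lacks.

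The cost is one sentence and a charter check, with no added visits or samples and no change to the sample size.

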
Assess safety of isatuximab SC and IV and local tolerability of isatuximab SC in combination with Pd.Characterize PK of isatuximab SC and IV in combination with Pd.Assess the delivery performance of the (investigational) device injector.	
Time to best response (TTBR): defined as the time from randomization to the date of first occurrence of IRC determined best overall response (PR or better) that is subsequently confirmed.Progression free survival (PFS): defined as the time from the date of randomization to the date of first documentation of progressive disease as determined by IRC or the date of death from any cause, whichever comes first. Responses will be determined according to IMWG criteria. Progression based on paraprotein will be confirmed based on two consecutive assessments. PFS will be censored at the date of the last valid disease assessment not showing disease progression performed prior to initiation of a further anti-myeloma treatment (if any) or the analysis cut-off date, whichever comes first. Patients with two or more consecutive missed assessments prior to PD or death will be censored at the last valid disease assessment. Details censoring rule will be provided in SAP.Overall survival (OS): defined as the time from the date of randomization to death from any cause. Participants without death prior to the analysis cut-off date will be censored at the last date the participant was known to be alive or the cut-off date, whichever is first.PFS2: defined as time from the date of randomization to the date of first documentation of PD (as assessed by investigator) after initiation of further anti-myeloma treatment or death from any cause, whichever happens first. Same censoring rule applies as in the PFS endpoint.Treatment-emergent adverse events (TEAEs)/serious adverse events (SAEs). Treatment-emergent adverse events (AEs) are defined as AEs that develop, worsen, or become serious during the treatment period. The treatment period is defined as the time from first dose of study treatment up to 30 days after last dose of study treatment.Laboratory parameters.Injection site reactions (ISRs) – SC arm only.Adverse events and laboratory parameters will be graded using NCI CTCAE v5.0.PK concentrations.Number of successful injections with (investigational) isatuximab injector device defined as completion of administration per provided instructions for use with no use errors or technical issues, divided by the total number of injections.

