Two consecutive assessments of laboratory parameters are needed. No known evidence of progressive disease or new bone/soft tissue lesions if radiographic studies were performed

- Serum and urine M-protein detectable by immunofixation but not on electrophoresis or, $\geq 90\%$ reduction in serum M-protein plus urine M-protein level <100 mg/24 h or,
- $\geq 90\%$ decrease in the sum of maximal perpendicular diameter compared to baseline in soft tissue plasmacytoma.
- FLC only: a $\geq 90\%$ decrease in the difference between involved and uninvolved FLC levels.

Two consecutive assessments are needed. No known evidence of progressive disease or new bone/soft tissue lesions if radiographic studies were performed

- $\geq 50\%$ reduction of serum M-protein and reduction in 24 hours urinary M-protein by $\geq 90\%$ or to <200 mg/24 h.
- If serum and urine M-protein are unmeasurable, a $\geq 50\%$ decrease in the difference between involved and uninvolved FLC levels is required in place of the M-protein criteria.
- In addition to the above listed criteria, if present at baseline, a $\geq 50\%$ reduction in the size (SPD) of soft tissue plasmacytomas is also required.

Two consecutive assessments are needed. No known evidence of progressive disease or new bone/soft tissue lesions if radiographic studies were performed

$\geq 25\%$ but $\leq 49\%$ reduction in serum M-protein and reduction in 24 h urine M-protein by 50%-89%, which still exceed 200 mg/24 h.

In addition to the above listed criteria, if present at baseline, $\geq 50\%$ reduction in size (SPD) of soft tissue plasmacytomas is also required.

No known evidence of progressive disease or new bone/soft tissue lesions if radiographic studies were performed

- Not meeting criteria for CR, VGPR, PR, MR or progressive disease.

Stable Disease **No known evidence of progressive disease or new bone/soft tissue lesions if radiographic studies were performed**

Any one or more of the following criteria:

Increase of $\geq 25\%$ from lowest confirmed value in any one of the following criteria:

- Serum M-protein (the absolute increase must be ≥ 0.5 g/dL).
- Serum M-protein increase ≥ 1 g/dL if the lowest M-component was ≥ 5 g/dL.
- Urine M-component (the absolute increase must be ≥ 200 mg/24 h).
- In patients without measurable serum and urine M-protein levels, the difference between involved and uninvolved FLC levels (absolute increase must be >10 mg/dL).

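### Appendix 11 sets two incompatible reference values for laboratory progression, and two conflicting plasmacytoma rules for VGPR

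*Protocol*

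**What the plan says.** All the response text is in Protocol Section 10.11 (Appendix 11).

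**Progression reference.** The progression criteria in Table 22 require a rise of at least 25% "from lowest confirmed value in any one of the following criteria", with a minimum absolute rise of 0.5 g/dL for serum M-protein. The reminder list after the table contains two adjacent bullets. The first says: "Percent increases for progression calculations are from lowest response values or baseline values, whichever is the smaller number", followed by "The lowest value does not need to be confirmed". The second says: "The lowest confirmed value before suspected progression will be used as baseline for calculation of progression".

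**Use of progression.** Table 6 in Section 3 defines PFS and DOR by IRC-determined progression or death. For PFS it adds: "Progression based on paraprotein will be confirmed based on two consecutive assessments". It also states: "PFS will be censored at the date of the last valid disease assessment not showing disease progression performed prior to initiation" of further anti-myeloma treatment, or the analysis cut-off.

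**VGPR with soft-tissue plasmacytoma.** In Table 22 the M-protein criterion for VGPR ends in *or*, and is followed by a decrease of at least 90%, described as a "decrease in the sum of maximal perpendicular diameter compared to baseline in soft tissue plasmacytoma". A note under the table says instead that participants who reach VGPR by other criteria must also show a lesion decrease of more than 90% in SPD (sum of products of perpendicular diameters). The PR criteria in the same table are already cumulative. Where a plasmacytoma is present at baseline, a "reduction in the size (SPD) of soft tissue plasmacytomas is also required".

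**The concern.** A single low reading that is not repeated is an ordinary event in serial M-protein data. One sentence lets that reading reset the reference for progression; two others do not. They cannot be reconciled by assigning one to the percentage and the other to the absolute rise, because Table 22 ties the 25% itself to the confirmed value. A reader of the protocol cannot tell which to apply.

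At stake are the occurrence and date of progression, and therefore PFS and DOR. If a participant starts further therapy when progression has been met under only one rule, the choice of rule also decides whether PFS records an event or a censored time.

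The VGPR wording raises a separate question: is lesion shrinkage a second way into VGPR, or an extra condition on it? VGPR or better is tested first among the key secondary endpoints (Section 9.2.5), and failure there stops the hierarchy.

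**Working it through.** The protocol gives no figure to reproduce here. The check applies each rule to the same assumed data.

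**1. Progression**

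Rule from Table 22: a rise of at least 25% and at least 0.5 g/dL over the reference. The level that triggers progression is therefore

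reference + max(0.25 × reference, 0.5).

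Assumed serum M-protein, g/dL: 3.0 (C1D1), 1.0, 1.0, 0.2, 0.75, 0.75; urine M-protein assumed below 100 mg/24 h.

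Change from baseline:
- 1.0: (1.0 − 3.0)/3.0 = −66.7%
- 0.2: (0.2 − 3.0)/3.0 = −93.3%
- 0.75: (0.75 − 3.0)/3.0 = −75.0%

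The 0.2 is one VGPR-level reading between PR-level readings. It is unconfirmed whether that term means a repeated value or a repeated response category.

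| | Lowest value, unconfirmed | Lowest confirmed value |
|---|---|---|
| Reference | 0.2 | 1.0 |
| Trigger level | 0.2 + 0.5 = 0.70 | 1.0 + 0.5 = 1.50 |
| Change at 0.75 | +0.55 g/dL, 0.55/0.2 = +275% | −0.25 g/dL, −25% |
| Result | Progression, confirmed by the second 0.75 | No progression |

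A second assumed series gives the same split: 3.0, 1.2, 0.9, 0.5, 0.9, 1.1, 1.1. From 0.5, the 1.1 is +0.6 g/dL (+120%), which is progression. From the confirmed 0.9 it is +0.2 g/dL (+22%), which is not.

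The lowest value can never exceed the lowest confirmed value, and the trigger level rises with the reference. The unconfirmed rule therefore gives the same progression date or an earlier one.

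**2. VGPR with plasmacytoma at baseline**

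Each text taken literally:

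| Participant | Table 22 (*or*) | Note under the table |
|---|---|---|
| M-protein VGPR, SPD falls by more than 90% | VGPR | VGPR |
| M-protein VGPR, SPD falls by 90% or less | VGPR | Not VGPR |
| No M-protein VGPR, Table 22 lesion criterion met | VGPR | Not VGPR |
| No M-protein VGPR, lesion criterion not met | Not VGPR | Not VGPR |

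The conflict is confined to the two middle rows. An example of the second row is M-protein −93.3%, confirmed, with an assumed lesion going from 4 × 4 to 2 × 2 cm. SPD falls from 16 to 4 cm², and (16 − 4)/16 = 75%. The table gives VGPR; the note does not.

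**The case against.** The best reply is that this is a wording matter with limited consequences. One IRC, blinded to arm, reads all cases under a charter (Section 4.9) that may already name a single rule. PFS and DOR are not formally tested. The series above are constructed, so they show that the calls can differ, not how often. The VGPR note can also be read as qualifying the *or* in the table.

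Most of that stands, and it sets the size of the point. It does not remove the conflict. The charter is not shown. Section 4.9 describes the IRC's role up to the primary analysis, whereas Section 4.8 plans a PFS update 15 months after the last patient in. Investigators also assess progression for PFS2. The protocol text needs to be usable without the charter.

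Stronger readings are tempting but not supported:

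- *The two lesion measures classify a wide band of lesions differently.* A reader might infer this from a lesion shrinking from 4 × 4 to 1.2 × 1.2 cm: summed diameters fall from 8.0 to 2.4 cm (70%), SPD from 16 to 1.44 cm² (91%). But with M-protein VGPR, that participant is VGPR under the table and under the note; without it, under neither. A difference arises only by joining the note's cumulative logic to the table's diameter sum, which neither text does. The table wording may simply have lost the word *products*.
- *The confirmation rules conflict.* The appendix speaks of the next time point, of same-day readings, and of a 4-week limit. The wording is untidy, but no participant is shown to be classified differently.
- *ORR is affected.* This would need a participant whose lesion and M-protein responses diverge so far that the PR criteria fail while the *or* route gives VGPR. Nothing in the protocol shows that this happens to any material extent.

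**Conclusion.** The progression conflict is established on the current text. Two sentences require a confirmed reference, one says confirmation is unnecessary, and the same series can be progression or not. The effect is on IRC-determined PFS and DOR. Both arms are read under the same criteria, so no directional bias between them is shown.

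The VGPR conflict is real but narrower. It concerns participants with M-protein VGPR whose SPD falls by 90% or less, and those who meet the table's lesion criterion without M-protein VGPR. It can affect the first key secondary endpoint. The protocol does not give the share of participants with soft-tissue plasmacytoma, so the number cannot be derived; it is probably small.

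The conclusion on progression rests on the wording alone. The numerical series are illustrations, and no reclassification rate is assumed. This should be corrected, but it does not threaten the co-primary analyses.

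**What to change.** Before the primary analysis:

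1. State one reference value for progression, confirmed or unconfirmed, in the Table 22 progression criteria and in both reminder bullets. Delete the sentence that contradicts it.
2. Rewrite the Table 22 lesion criterion for VGPR to match the note: cumulative when a plasmacytoma is present at baseline, measured by SPD, with one threshold. The PR criteria already follow this pattern.
3. Align the IRC charter and apply the single rule to all cases, including those already read.

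The cost is a few sentence edits in Appendix 11, a charter update and a re-application of the rule to existing reads. No new data are needed. Doing it now avoids choosing a progression rule once results are known.
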